5.9.3 Total Exposure to Study Drug for Each Subject

Total exposure to study drug for each subject for Treated Population will be calculated as duration of non-flare-up treatment and flare-up treatment (see Section 3.2.3 and 3.2.4 for calculation).

Total actual dose (mg) will be summarized by Enrolled Population.

- Total dose is calculated as the cumulative dose (mg) across all dosing regimens (non-flare-up and flare-up) for each subject.
- Total non-flare-up dose is calculated as the cumulative dose across all the non-flare-up treatment periods.
- Total flare-up dose is calculated as the cumulative dose taken across all flare-up cycles.
- All total dose calculations account for weight-adjusted doses, dose reductions

5.9.4 Duration of Subject Participation in Part C

Duration (months) of participation in Part C is calculated as (the earlier date of completion of Part C or discontinuation - the date of informed consent + 1)/30.5. For subjects ongoing, it is calculated as (data cutoff date – date of informed consent + 1)/30.5.

Number and percentage of subjects will be summarized for following duration categories for Enrolled Population:

- ≤ 6 months
- >6 to 12 months
- >12 to 18 months
- >18 to 24 months
- >24 months

5.9.5 Duration of Subject Participation in Part D

- up to 24 months

5.10 Compliance

Compliance is defined as (duration of treatment/expected duration of treatment). Calculation of duration of treatment is described in Section 3.2.3 and 3.2.4.

The expected duration of treatment is calculated as following:

- For non-flare-up treatment, expected duration of treatment is calculated as (last non-flare-up dose date – first non-flare-up dose date) – (sum of (all Flare-up cycle dosing periods)) + 1.
- For flare-up treatment, expected duration of treatment is calculated as total of expected flare-up cycle dosing periods across all flare-up cycles. Each expected flare-up cycle dosing period is defined as (last flare-up cycle dose date – first flare-up cycle dose date + 1).

Compliance will be summarized for the Treated Population with descriptive statistics. Compliance in category (<80%, ≥80%) will also be summarized for counts and percentages of subjects.

6 Efficacy Data

Unless otherwise stated, efficacy data will be summarized using Enrolled Population presented by groups: PVO 20/10 mg Only, PVO 5 mg, PVO Total and Never Received PVO Treatment. The PVO 20/10 mg Only group only includes subjects who did not take PVO 5 mg.

Imaging Reads

Imaging data includes results from low-dose WBCT scans (excluding head) and radiographs.

WBCT HO status and total HO volume or new HO volume will be summarized by visit. Those analysis will be included in the interim CSR. All other analysis will be presented in the final CSR.

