6.10 Compliance

Compliance to study drug for each treated flare-up will be calculated based on the number of actual capsules taken and the expected number of capsules as specified in the protocol for 42 days of dosing. The number of actual capsules will be calculated as the number of capsules dispensed – the number of capsules returned – the number of capsules lost. For example, a subject who took 10 capsules and was expected to take 42 capsules would be $10/42 = 23.8\%$ compliant.

Percent compliance will be summarized for the Treated Population with descriptive statistics. Categories of percent compliance ($<80\%$, $\geq 80\%$) will be summarized for the Treated Population with counts and percentages of flare-ups.

7 Efficacy Data

Efficacy assessments at Flare-up Component visits will generally be presented in total for the Efficacy Population. The primary efficacy analysis and selected other efficacy analyses will also be presented for the PP Population. Efficacy assessments at Follow-up Component visits will be listed.

Imaging Reads

Imaging data includes results from CT scan, x-ray, MRI, and US. Results will be read and interpreted using two different review processes (Primary Read and Global Read) as described in the study protocol.

The Primary Read review will be performed by two independent musculoskeletal radiologists during the study as images are made available. If there is sufficient agreement between the

independent reviews, both will be used for analysis. If there is insufficient agreement between the independent reviews, an adjudication review will be performed and used for analysis. Imaging procedures performed (yes, yes but not evaluable, no) will be summarized at scheduled visits with counts and percentages of subjects or flare-ups as appropriate.

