5.9 Compliance

Overall compliance to study drug will be calculated for each subject based on actual study drug taken (mg) and the expected study drug taken (mg) over the course of Part B.

Actual study drug taken will be calculated as the sum of study drug taken from each bottle where study drug taken from each bottle is the number of capsules taken multiplied by capsule strength.

Expected study drug taken will be calculated based on the protocol-defined treatment regimen. Subjects experiencing eligible flare-ups are expected to take 20 mg for 28 days followed by 10 mg for 56 days (or longer if treatment is extended). If the number of days of treatment is extended, weight-adjusted doses, and dose reductions should be taken into account in this calculation. Subjects in the Adult Cohort who are taking non-flare-up treatment are expected to take 5 mg each day they are not taking flare-up based treatment.

For example, if a subject in the Adult Cohort took 90 5-mg capsules from bottle 1, 28 20-mg capsules from bottle 2, and 50 10-mg capsules from bottle 3, then the actual study drug taken is equal to $90 \times 5 + 28 \times 20 + 50 \times 10 = 1510$ mg. The subject started non-flare-up based treatment on Study Day 1, started flare-up based treatment on Study Day 11, and completed Part B on Study Day 174. Treatment was not extended for this flare-up, and doses were not weight-adjusted or reduced. Therefore, the subject was expected to take 20 mg for 28 days followed by 10 mg for 56 days for the flare-up and 5 mg for 90 days (174 total days in Part B – 84 days of flare-up based treatment). Expected study drug taken = $90 \times 5 + 28 \times 20 + 56 \times 10 = 1570$ mg. Compliance would be calculated as: $1510 \text{ mg} / 1570 \text{ mg} = 96.2\%$.

Percent compliance will be summarized for the Treated Population with descriptive statistics. Categories of percent compliance ($<80\%$, $\geq 80\%$) will be summarized for the Treated Population with counts and percentages of subjects.

6 Efficacy Data

Efficacy data for flare-up based treatment assessments will generally be presented by the following treatment groups for the Flare-up Population: PVO 20/10 mg, Prior Non-Flare-up/PVO 20/10 mg, and Combined PVO 20/10 mg. The primary efficacy analysis and other selected efficacy analyses will also be performed using the Flare-up PP Population.

Imaging Reads

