Based on additional post-hoc analyses presented to the DMC on January 21, 2020, the DMC noted that using the square-root transformation of the data in the primary analysis appears to have moved the statistical conclusion from significant therapeutic benefit to showing futility of the treatment. The DMC also noted that the dilemma created by these highly disparate results precludes a confident conclusion about futility. As such, the DMC recommended that additional analyses be conducted and provided to them for consideration at the next interim analysis.

US FDA instituted a partial clinical hold on dosing of palovarotene due to premature physéal closure (PPC) for subjects <14 years of age on December 4, 2019; as of the finalization of this SAP amendment, dosing

has not yet resumed for these subjects. Dosing on all other subjects in Study 301 and Study 202 Part C not subject to US FDA's partial clinical hold was interrupted following the January 21, 2020 DMC meeting while the protocol amendment allowing the continuation of the study after the futility outcome and incorporating the additional analyses requested by the DMC was reviewed by regulatory agencies, IRBs, and investigational sites. These subjects had palovarotene dosing interrupted on or around January 24, 2020. The sponsor allowed dosing to resume as of March 26, 2020, provided each individual site had obtained Ethics Committee approval to do so and the site was able to fulfil regulatory and operational requirements. Subjects were expected to restart dosing over a span of weeks due to these logistical considerations.

2 Overview

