2.3 Study Treatment

As of 04 December 2019, all subjects <14 years of age were required to interrupt study drug due to a partial clinical hold placed on the palovarotene clinical development program by the US FDA. Treatment will subsequently not be restarted in children < 14 years of age.

Subjects and/or their parents/caregivers will report potential flare-up symptoms to site personnel; such symptoms include, but are not limited to, pain, swelling, redness, decreased range of motion, stiffness, and warmth. Only one symptom is required to define a flare-up. If these symptoms are consistent with previous flare-ups, include a subject reported onset date, and are confirmed by the Investigator as associated with a flare-up, subjects will receive open-label palovarotene treatment as follows:

- 20 mg for 4 weeks (28 days) once daily. The first dose will be taken upon flare-up confirmation by the Investigator. To be followed by:
- 10 mg for 8 weeks (56 days) once daily, for a total flare-up treatment duration of 12 weeks (84 days); 10 mg treatment may be extended if the flare-up is ongoing and continue until the flare-up resolves. Dosing will be extended in 4-week intervals and be based on clinical signs and symptoms as assessed by the Investigator.

Flare-up based dosing should also be initiated if the Investigator confirms the presence of a substantial high-risk traumatic event likely to lead to a flare-up.

All dosing, regardless of non-flare-up or flare-up based, will be weight-adjusted in subjects under the age of 18 years with less than 90% skeletal maturity on hand/wrist radiography at Screening. (Note: all weight-based dosing will cease when subjects achieve $\geq 90\%$ skeletal maturity based on hand/wrist radiography, but radiographic assessment of the growth plate will continue until these subjects achieve 100% skeletal maturity at both knee and hand/wrist locations.)

Table 1: Weight-Adjusted Palovarotene Doses and Dose De-Escalation Doses

Weight Range Category	20-mg Equivalent	15-mg Equivalent	10-mg Equivalent	7.5-mg Equivalent*	5-mg Equivalent*	2.5-mg Equivalent*
20 to <40 kg	12.5 mg	10 mg	6 mg	4 mg	3 mg	1.5 mg
40 to <60 kg	15 mg	12.5 mg	7.5 mg	5 mg	4 mg	2 mg
≥ 60 kg	20 mg	15 mg	10 mg	7.5 mg	5 mg	2.5 mg

* In the event of dose de-escalation from 20-mg, 10-mg, or 5-mg equivalent, respectively.

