3.2.3 Duration of Flare-up Treatment

For subjects receiving flare-up treatment, duration of flare-up treatment (days) is defined as total flare-up cycle dosing periods (days) across all flare-up cycles.

For a flare-up cycle, the flare-up cycle dosing period (days) is defined as days that subjects received flare-up based treatment and is calculated as (last dose date of the flare-up cycle – first date of the flare-up cycle – days where flare-up meds were not taken/interrupted during the flare-up cycle + 1).

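### Part C flare-up compliance divides by the days from first to last dose actually taken, so stopping a course early cannot lower it; imposed hold days count against 5 mg restarters

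*SAP*

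**What the plan says.** In Part C, 5.10 states: "Compliance is defined as (duration of treatment/expected duration of treatment"). For flare-up treatment the denominator is totalled over cycles, and "Each expected flare-up cycle dosing period is defined as (last flare-up cycle dose date – first flare-up cycle dose date + 1"). The numerator comes from 3.2.3, which gives each cycle's dosing period by this formula: "last dose date of the flare-up cycle – first date of the flare-up cycle – days where flare-up meds were not taken/interrupted during the flare-up cycle + 1". The results are then split: "Compliance in category (<80%, ≥80%) will also be summarized for counts and percentages of subjects".

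The planned course is in Part C 2.3: 28 days at the higher dose, then 56 at the lower, "for a total flare-up treatment duration of 12 weeks (84 days"), with extensions in 4-week steps and a restart of the regimen at an intercurrent flare-up or high-risk trauma.

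The other two plans use the planned regimen as denominator. Part A (6.10) uses "the expected number of capsules as specified in the protocol for 42 days of dosing". Part B (5.9) says: "Expected study drug taken will be calculated based on the protocol-defined treatment regimen", and takes account of extensions, weight-adjusted doses and dose reductions.

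For 5 mg dosing, Part C 3.2.4 subtracts days not taken or interrupted from the duration, while the expected duration in 5.10 removes only the flare-up cycle periods. Section 1.2 describes the pause for subjects not under the partial clinical hold: "These subjects had palovarotene dosing interrupted on or around January 24, 2020", with resumption allowed from 26 March 2020.

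**The concern.** A denominator called expected should say how much treatment was planned. Here it says how long the subject happened to stay on drug. The flare-up figure can register missed days inside a course but not abandonment of it, although the table and its 80% split will be read as adherence to the 20/10 mg regimen.

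The non-flare-up figure has the opposite fault. A subject who obeyed an imposed stop and later restarted is scored as having missed those days. One table would thus overstate compliance for abandoned flare-up courses and understate it for subjects who complied with a hold. Part C keeps the name and the 80% cut-off used in Parts A and B but changes the meaning, and neither table of changes in the Part C SAP (sections 10 and 11) mentions it.

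**Working it through.** Part C gives no worked compliance example to reproduce. The examples in the other parts do reproduce: Part A, 10/42 = 23.8%; Part B, 1510/1570 mg = 96.2%.

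**Flare-up formula.** Let a cycle run from day 1 to last dose day L, with g days not taken.

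- Numerator (3.2.3): L − 1 − g + 1 = L − g
- Denominator (5.10): L − 1 + 1 = L
- Compliance: (L − g)/L = 1 − g/L

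The 84 days do not appear. The last dose date in 5.10 cannot reasonably be read as a scheduled date, because 3.2.3 uses the same term for treatment received.

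**One cycle, no extension or restart, no gaps (g = 0):**

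| Last dose day | Part C 5.10 | Against 84 days |
|---|---|---|
| 10 | 10/10 = 100% | 10/84 = 11.9% |
| 28 | 28/28 = 100% | 28/84 = 33.3% |
| 60 | 60/60 = 100% | 60/84 = 71.4% |
| 67 | 67/67 = 100% | 67/84 = 79.8% |
| 68 | 68/68 = 100% | 68/84 = 81.0% |

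Since 0.8 × 84 = 67.2, stops up to day 67 belong below 80% but are placed at or above it. Only gaps lower the figure: an 84-day span with 17 missed days gives 67/84 = 79.8%.

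**Several cycles.** Section 5.10 sums over cycles and classifies subjects, so the misplaced range shrinks when earlier cycles were complete.

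- One full cycle plus a stop at day 10: 94/94 = 100% under 5.10, 94/168 = 56.0% against plan; misplaced.
- One full cycle plus a stop at day 50: 134/168 = 79.8% against plan; misplaced.
- One full cycle plus a stop at day 51: 135/168 = 80.4%; category correct.
- One full cycle plus a stop at day 60: 144/168 = 85.7%; category correct, though 5.10 still shows 100%.
- Two full cycles plus a stop at day 34: (168 + 34)/252 = 80.2%; category correct.
- Four full cycles plus a stop at day 1: (336 + 1)/420 = 80.2%; category correct at any stopping day.

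**Non-flare-up formula.** From 24 January to 26 March 2020 is 62 days. For a 5 mg subject who restarted, was in no flare-up cycle during the pause and missed nothing else, a dosing span of S days gives (S − 62)/S.

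- S = 310: 248/310 = 80.0%, so any shorter span falls below 80% because of the pause alone.
- S = 365: 303/365 = 83.0%.
- S = 1095 (3 × 365): 1033/1095 = 94.3%.

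The non-flare-up denominator also ends at the last dose taken, so it too is blind to early stopping.

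**The case against.** The strongest reply is that the SAP reports early stopping elsewhere. Section 5.1 gives treatment discontinuations with reasons. Section 5.7 counts cycles and subjects with drug discontinued, interrupted or reduced, overall and by high or low dosing. Section 5.9.1 bands duration per cycle, so a 10-day course appears in the ≤2-week band. Section 7.1 tabulates and lists adverse events leading to discontinuation. This stands. A reader might infer that toxicity-driven stopping would be hidden, or that HO and adverse-event results would be credited to a regimen not taken; these tables answer that, and nothing in the document shows that many subjects stopped early.

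Nor does a planned efficacy analysis depend on compliance. The 80% cut-off belongs to the Flare-up Per Protocol Population, for which 4.4 plans no formal analysis. What remains is the listing of that population in 5.7.

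Adherence while on treatment is also a legitimate measure in its own right, and 2.3 itself directs discontinuation in some circumstances; a bare 84-day denominator would mark such a subject non-compliant. That argues for a stated rule and a clear label. It does not justify calling an observed span expected.

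Non-comparability with Parts A and B carries limited weight, because those two already differ (capsules per flare-up against mg per subject) and no cross-part compliance comparison is planned.

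**Conclusion.** The definition should be changed, but the consequence is limited. As written, 5.10 gives a wrong flare-up compliance figure for anyone who stops a course early, and can give a wrong <80%/≥80% category. The figures of 11.9%, 33.3% and 71.4%, and the day-67 limit, assume a single unextended cycle without restart or gaps.

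Two stronger readings are not supported. A reader might infer that every gap-free stop before day 68 is misclassified; summation over cycles rules that out, as the day-60 example after a full cycle shows. A reader might also take 62 days as the minimum loss for every restarter. The interruption date is approximate, sites resumed over a span of weeks, a subject in a flare-up cycle at the pause is affected differently, and some subjects did not receive 5 mg at all. Roughly 62 days or more for a restarter on 5 mg, subject to actual dates, is as far as the document goes.

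The effect is confined to the descriptive compliance table, its 80% split and any use of the Flare-up Per Protocol Population in 5.7.

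**What to change.** In Part C 5.10:

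- Set expected flare-up days per cycle to the SAP's own planned course: 84 days plus documented extensions, re-counted at each documented restart of the regimen, and summed over cycles.
- Exclude sponsor- or regulator-imposed hold days from expected days, for flare-up and non-flare-up treatment alike.
- State one rule, applied to both, on how protocol-directed discontinuations count.
- If the current ratio is kept, report it in addition and label it adherence while on treatment.

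The cost is SAP wording and the reprogramming of one derived variable, using dates already collected. Reported flare-up compliance will be less favourable wherever courses ended early.

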6.1 Primary Efficacy Endpoint

The primary efficacy endpoint is the annualized change in new HO volume as assessed by low-dose WBCT scan (excluding head) during Part C.

The change in new HO total volume will be compared to baseline where the baseline value was performed prior to the initiation of non-flare-up based dosing (in Part B or Part C).

The WBCT HO total volume will be calculated as the sum of the volumes for each location of the WBCT assessment. If there is no HO, 0 will be assigned for analysis.

The annualized change in new HO volume will not be summarized in the interim CSR for the palovarotene NDA, due to the ongoing nature of the reads. This analysis will be included in the final CSR. However, all WBCT data (total and by region) HO volume, HO status, New HO volume by visit will be listed.

Annualized HO will be summarized before the pause in palovarotene dosing, i.e. 4 December 2019 for patients younger than 14 years old or 24 January 2020 due to the crossing of the futility boundary in Study PVO-1A-301; and after restarting palovarotene.

Inferential analyses are described in Section 3.4 Adjustment for Covariates.

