4.1 Enrolled Population

The Enrolled Population will include all subjects enrolled in Part C.

Unless stated, analysis for Enrolled Population will be presented by groups: PVO 20/10 mg Only, nonflare-up PVO 5 mg, PVO total, and Never Received PVO Treatment. The PVO 20/10 mg Only group only includes subjects who didn't take PVO 5 mg.

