5.8 Annualized Flare-up Rate

Flare-ups are counted using the number of subject/Investigator-reported flare-ups (including intercurrent flare-ups). Rates will be calculated as the total number of flare-ups divided by duration of follow-up (year). The duration of follow-up (years) is defined as (last date on study – Part C Study Day 1 + 1)/365.25. Flare-up rate will be calculated separately for pre-interruption, during interruption, and after re-start of palovarotene dosing.

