6.2 Secondary Efficacy Endpoints

Secondary efficacy endpoints for include:

1. Percent of subjects with new HO at Months 12, 24, 36, and overall.
2. Change from baseline in ROM as assessed by CAJIS at Months 6, 12, 18, 24, 30, and 36.
3. Change from baseline in physical function using age-appropriate forms of the FOP-PFQ at Months 6, 12, 18, 24, 30, and 36.
4. Change from baseline in physical and mental function for subjects ≥ 15 years old and mental function for subjects < 15 years old using age-appropriate forms of the PROMIS Global Health Scale at Months 6, 12, 18, 24, 30, and 36.

Secondary endpoints will also be summarized before the pause in palovarotene dosing and after restarting palovarotene.

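### Part C: the before-pause and after-restart summaries of HO, secondary endpoints and flare-up rate rest on different subjects, and no same-subject summary is specified

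*SAP*

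**What the plan says.** All references are to the Part C SAP.

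- **Default population.** Section 6 (Efficacy Data) states: "Unless otherwise stated, efficacy data will be summarized using Enrolled Population presented by groups". Section 4.1 defines that set: "The Enrolled Population will include all subjects enrolled in Part C".
- **Primary endpoint.** Section 6.1: "Annualized HO will be summarized before the pause in palovarotene dosing", with the pause dated 4 December 2019 for patients younger than 14 and 24 January 2020 for the interruption that followed the Study 301 futility result, "and after restarting palovarotene". It names no other population and sends inference to Section 3.4.
- **Secondary endpoints.** Section 6.2: "Secondary endpoints will also be summarized before the pause in palovarotene dosing and after restarting palovarotene".
- **Flare-up rate.** Section 5.8: "Flare-up rate will be calculated separately for pre-interruption, during interruption, and after re-start of palovarotene dosing". It names no population.
- **Restart rule.** Section 2.3: "Treatment will subsequently not be restarted in children < 14 years of age". Section 3.1.4 nevertheless defines a restart baseline that covers subjects paused under the under-14 hold who later resumed.
- **Post-restart set.** Section 4.6 (RFAS) requires restart after January 2020 and two HO volumes from restart onwards, the first scan 30 days or more clear of the preceding flare-up.

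**The concern.** The two columns for each endpoint do not describe the same people. Under-14s are placed explicitly in the pre-pause HO summary by their own cut date. They can reach the post-restart summary only if they restarted later, which Section 2.3 does not allow while they are under 14. Age is not the only filter. Section 1.2 made resumption depend on ethics approval and site capability, Section 1.1 acknowledges subjects who did not restart, and the RFAS, where used, adds scan conditions that the pre-pause summary does not carry.

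Readers of the final report will set the two periods side by side. A lower or higher HO rate, flare-up rate, CAJIS or FOP-PFQ change after restart would then mix any real change with the departure of children and other non-restarters. Nothing in 5.8, 6.1 or 6.2 fixes a common cohort, a within-subject difference or an age split that would separate the two.

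**Working it through.** The plan states no figure on this point, so there is none to reproduce. The check has two parts.

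**1. Who contributes to each period**

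| Summary | Before the pause | After restart |
|---|---|---|
| Annualized HO (6.1) | Enrolled Population by default; under-14s explicitly included | Restarters only |
| Secondary endpoints (6.2) | Enrolled Population by default | Restarters only |
| Flare-up rate (5.8) | No population named | Restarters only |

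The flare-up rate has a third period, the interruption. Section 1.2 records that under-14s were held first and that dosing in all other Part C subjects stopped around 24 January 2020. The pre-interruption and interruption rates therefore start from largely the same people, children included. Composition shifts there only if person-time is pooled. If non-restarters are a share g of subjects and their interruption follow-up is k times that of restarters, their weight in the pooled interruption rate is gk/(gk + 1 - g), which exceeds g whenever k is above 1. Section 5.8 does not say whether person-time is pooled.

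**2. How large the composition effect could be**

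Assumed inputs, because the documents give neither:

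- f = share of pre-pause contributors who were under 14 and never restart, 0.1 to 0.4;
- r = ratio of the mean annualized rate in under-14s to that in older subjects, 0.5 to 3.

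Every subject's own rate is held constant, and all older subjects are taken to restart. With the older subjects' mean set to 1:

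- pre-pause mean = f·r + (1 - f)
- post-restart mean = 1
- apparent change = 1/(f·r + 1 - f) - 1

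Example: f = 0.2, r = 2 gives a pre-pause mean of 0.4 + 0.8 = 1.2 and a change of 1/1.2 - 1 = -16.7%.

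| f | r = 0.5 | r = 1 | r = 1.5 | r = 2 | r = 3 |
|---|---|---|---|---|---|
| 0.1 | +5.3% | 0% | -4.8% | -9.1% | -16.7% |
| 0.2 | +11.1% | 0% | -9.1% | -16.7% | -28.6% |
| 0.3 | +17.6% | 0% | -13.0% | -23.1% | -37.5% |
| 0.4 | +25.0% | 0% | -16.7% | -28.6% | -44.4% |

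With the approximately 60 subjects of Section 2.4, the post-restart number would be about 54, 48, 42 or 36 for f = 0.1, 0.2, 0.3 or 0.4, before any loss through other non-restart or the RFAS scan rule.

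If the pre-pause mean is taken over the later restarters only, both means are 1 and the apparent change is 0% for every f and r.

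**The case against.** The strongest reply is that no before/after comparison is planned. Sections 6.1 and 6.2 call for summaries and 5.8 for separate rates. No difference, test or decision links the periods, and the SAP nowhere calls the pre-pause period a benchmark. Inference goes to Section 3.4, where Part C is compared with the natural history study in models that include baseline age and by propensity scores. Sections 1.1 and 10 put the weight of the final report on later data. All this stands: the issue is how paired descriptive results are read, and no error rate is affected. But the age adjustment in 3.4 does not touch the before/after columns.

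Three stronger readings are tempting and are not supported:

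- A reader might infer that the pre-interruption versus interruption flare-up rates are confounded in the same way. They are not, since both start from largely the same subjects.
- A reader might infer that every child paused under the hold is lost for good. Section 3.1.4 provides for some of them restarting, and follow-up ran to late 2022, so f is the share who never restart and may be well below the share under 14 at the pause.
- A reader might infer that every enrolled subject sits in one pre-pause figure. Section 6 reports by treatment group, with a separate column for subjects never given the drug in Part C, who have no pause; for 5.8, all enrolled subjects would be an inference.

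It can also be said that 3.12 permits exploratory analyses by age and 5.4 tabulates age for every population. The former is optional. The latter cuts at 15 and 18, not 14, and describes populations rather than periods. Neither aligns the cohorts. The bone safety section (7.9) does state who contributes to its off-treatment and new-baseline growth assessments, so the SAP can do this where it chooses.

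**Conclusion.** The point holds as a weakness in descriptive summaries. For HO and the secondary endpoints, the pre-pause column defaults to the Enrolled Population with under-14s included, the post-restart column can hold only restarters, and nothing in the plan puts the same subjects in both. For the flare-up rate, no population is named and no common cohort is set; the concern applies to comparisons with the post-restart period, and to pre-interruption versus interruption only through the weight of non-restarters' longer follow-up if person-time is pooled.

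A reader might infer that a fall after restart would be spurious, or might take one figure from the table as an estimate. The documents support neither. They give no age mix among non-restarters and no rate by age, so both size and direction are unknown. The range of about +25% to -44% rests wholly on the assumed f and r. It shows that the effect could be material, not that it is. The age component vanishes if r = 1. The change is worth making because it is cheap, but it does not undermine the planned comparisons with the natural history study.

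**What to change.** In Sections 5.8, 6.1 and 6.2:

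1. Name the population and report the number contributing in each period.
2. Add pre-pause columns, and for the flare-up rate interruption columns, restricted to subjects who contribute post-restart data. Give within-subject differences, and base any before/after statement on this set.
3. Keep the all-enrolled pre-pause summary, split by age at the pause (under 14; 14 or over), and show non-restarters separately.
4. Reconcile Sections 2.3 and 3.1.4 on whether subjects paused under the under-14 hold could restart, so that the post-restart set is unambiguous.

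The cost is SAP wording and a few table columns from data already held. The same-subject group will be smaller and its pre-pause estimates less precise. The restriction removes the change of population but not ageing between the periods, nor the difference in baseline: before first non-flare-up dosing in 6.1, first assessment after restart in 3.1.4. Where the RFAS is used, its 30-day scan condition also remains a difference. The tables should state these limits.
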